4.2. Participant Dispositions

A detailed description of participant disposition will be provided at the end of the study.

Frequency counts and percentages of all participants screened, enrolled, randomized, and receiving at least 1 dose of study drug will be summarized by treatment group, if applicable. Of the randomized population, frequency counts and percentages of participants who completed the study or prematurely discontinued the study (and/or study drug), including the reason for premature discontinuation, will be summarized by treatment group.

The study completion status for the randomized population is defined as following: participants with status reported via electronic case report form (eCRF) as “Completed” at the follow-up visit (Visit 801) will be considered as completers; otherwise, participants will be considered as noncompleters. A Kaplan-Meier analysis of time from randomization to premature discontinuation from the study and/or study treatment by treatment group will be provided.

A similar summary for the intensive lifestyle modification lead-in period can be found in Appendix 4 (Section 6.4).

4.3. Primary Endpoints Analysis

For submission of Study GPHM to the US FDA to support the registration of tirzepatide for chronic weight management, both primary efficacy assessments will be guided by the treatment regimen estimand conducted using the FAS. Assessment of the primary objectives will be conducted with multiple imputation of missing data (see Section 4.3.2.3).

For other regulatory agencies, publications, and other purposes, the assessment of efficacy objectives may be guided by the efficacy estimand using the EAS.

4.3.1. Definition of Endpoint

The primary efficacy measure will be percent change in body weight AND percentage of participants who achieve $\geq 5\%$ body weight reduction from randomization at 72 weeks. The percent change in body weight at each nominal visit is defined as follows:

$$\frac{(\text{postbaseline body weight [kg]} - \text{baseline body weight [kg]})}{\text{baseline body weight [kg]} * 100.}$$

Both percent change in body weight and percentage of participants who achieve $\geq 5\%$ body weight reduction will be summarized by treatment and nominal visit (week) from randomization to 72 weeks.

4.3.2. Main Analytical Approach

4.3.2.1. The Analysis Related to the Treatment Regimen Estimand

The analysis related to treatment regimen estimand will be conducted using data in the FAS.

The analysis for the mean percent change in body weight will be conducted utilizing ANCOVA. The response variable for the ANCOVA model will be percent change in body weight from randomization at 72 weeks. A logistic regression model will be used for the analysis of the percentage of participants achieving at least 5% body weight reduction obtained at the 72-week visit. Both models will include terms of treatment group, country/pooled country, and sex as fixed effects and baseline body weight as a covariate. The ANCOVA analysis will be conducted with hybrid imputation of missing body weight at 72 weeks (see Section 4.3.2.3 for details) and statistical inference over multiple imputation of missing data guided by Rubin (1987). For the

logistic regression, missing body weight data at 72 weeks will be imputed first, based on Section 4.3.2.3, then the continuous measurements will be categorized into status of achieving at least 5% body weight reduction (Yes or No).

With the aid of the ANCOVA model, the 2-sided 95% CI for mean change in percentage of body weight from baseline to the Week 72 visit between tirzepatide MTD and placebo will be derived.

With the aid of the logistic regression model, the 2-sided 95% CI and odds ratio for percentage of participants achieving at least 5% body weight reduction from baseline to the Week 72 visit between tirzepatide MTD and placebo will be derived.

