## 6.3. Measures to Minimize Bias: Randomization and Blinding

This is a double-blind, randomized study.

Participants who meet all criteria for enrollment will undergo a 12-week intensive lifestyle modification lead-in period. Those who achieve  $\geq 5.0\%$  weight loss at Visit 10 will be randomized to one of the study treatment groups (tirzepatide MTD or placebo) for the duration of the treatment period. Assignment to treatment groups will be determined by a computer-generated random sequence using an IWRS. Participants will be randomized in a 1:1 ratio to receive tirzepatide MTD or placebo.

The randomization will be stratified by country, sex (female, male), and percent weight loss at the end of lead-in ( $<10\%$  versus  $\geq 10\%$ ).

Investigators, site staff, clinical monitors and participants will remain blinded to the treatment assignments until the study is complete.

Emergency unblinding for AEs may be performed through the IWRS. This option may be used ONLY if the participant's well-being requires knowledge of the participant's treatment assignment. All emergency unblinding events are recorded and reported by the IWRS.

If an investigator, site personnel performing assessments, or participant is unblinded, the participant must be discontinued from the study. In cases where there are ethical reasons to have the participant remain in the study the investigator must obtain specific approval from a Lilly clinical research physician (CRP) for the participant to continue in the study.

In case of an emergency, the investigator has the sole responsibility for determining if unblinding of a participant's treatment assignment is warranted for medical management of the event. The participant's safety must always be the first consideration in making such a determination. If a participant's treatment assignment is unblinded, Lilly must be notified immediately. If the investigator decides that unblinding is warranted, it is the responsibility of the investigator to promptly document the decision and rationale and notify Lilly as soon as possible.

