### 9.4. Statistical Analyses

#### 9.4.1. General Considerations

Statistical analysis of this study will be the responsibility of Lilly or its designee. Any change to the data analysis methods described in the protocol will require an amendment ONLY if it changes a principal feature of the protocol. Any other change to the data analysis methods described in the protocol, and the justification for making the change, will be described in the statistical analysis plan (SAP) or the clinical study report (CSR). Additional exploratory data analyses may be conducted as deemed appropriate.

Unless otherwise noted, all tests of treatment effects will be conducted at a 2-sided alpha level of 0.05, and the confidence interval (CI) will be calculated at 95%, 2-sided. In statistical summaries and analyses, data will be analyzed as randomized.

Unless specified otherwise, efficacy analyses will be conducted using efficacy analysis set (EAS) and safety analyses will be conducted using safety analysis set (SS).

Unless otherwise specified, for analyses in the double-blind period, baseline is defined as the last non-missing data collected prior to or at randomization (prior to first dosing of study drug); for analyses in the lead-in period, baseline is defined as the last non-missing data collected prior to or at study entry (Visit 1 and Visit 2).

Summary statistics for continuous measures will include sample size, mean, SD, median, minimum, and maximum. The analysis model to make comparisons among treatment groups relative to continuous measurements assessed over time will be a mixed model for repeated measures (MMRM), with terms of treatment, visit, treatment-by-visit interaction, stratification factors and baseline measurement as a covariate. An unstructured covariance structure will model relationship of within-patient errors.

Kaplan-Meier method will be used for estimation of cumulative event-free survival rates over time, and cox proportional hazards regression analysis will be used to compare hazard rates among treatments.

Summary statistics for categorical measures (including categorized continuous measures) will include sample size, frequency, and percentages. Logistic regression will be used to examine the treatment difference in binary efficacy outcomes if there is a need to adjust for covariates. Otherwise, Fisher's exact test will be used to examine the treatment difference in categorical outcomes.

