### 9.4.3. Efficacy Analyses

#### 9.4.3.1. Primary Analyses

There will be 2 estimands of interest in comparing efficacy of tirzepatide MTD with placebo. For the FDA, the primary efficacy analysis will be guided by the “hybrid” estimand and will be conducted using the FAS. This assessment will analyze percent change in body weight obtained at the 72-week visit using an analysis of covariance (ANCOVA) and the percentage of participants achieving at least 5% body weight reduction obtained at the 72-week visit using a logistic regression model. Both models (ANCOVA and logistic regression model) will include terms of treatment, stratification factors, and baseline body weight as a covariate. Missing data solely due to a pandemic or natural disaster (after other reasons for missing data are ruled out) will be considered missing at random, and missing data will be imputed using all non-missing data of the primary outcome measurement from the same treatment arm. Missing data of the primary outcome measurement due to all other Intercurrent Events (ICEs) will be imputed based on retrieved dropouts in the same treatment arm, defined as observed primary outcome measurements from participants in the same treatment group who had their efficacy assessed after early discontinuation of study drug. In cases where there are not enough retrieved dropouts to provide a reliable imputation model (for example, the model implemented by the SAS program does not converge), an alternative multiple imputation method with reference to the placebo group (that is, placebo multiple imputation) will be used. Analysis will be conducted with multiple imputations.

For all other purposes, the primary efficacy analyses will be guided by the “efficacy” estimand, which represents efficacy prior to discontinuation of study drug, and conducted using the EAS. The primary analysis model will be an MMRM for body weight percentage change over time and a longitudinal logistic regression for proportion of participants achieving at least 5% body weight reduction over time. The response variable of the MMRM will be the percent change in body weight from baseline values obtained at each scheduled post baseline visit. The response variable of the longitudinal logistic regression will be the proportion of participants achieving at least 5% body weight reduction at each scheduled post randomization visit. The Kenward-Roger approximation will be used to estimate denominator degrees of freedom.

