4.1. General Considerations

Statistical analysis of this study will be the responsibility of Eli Lilly and Company (Lilly) or its designee. Some analyses and summaries described in this analysis plan may not be conducted if not warranted by data (for example, few events to justify conducting an analysis). Additional analyses of the data may be conducted as deemed appropriate.

Unless otherwise noted, all tests of treatment effects will be conducted at a 2-sided alpha level of 0.05, and the confidence interval (CI) will be calculated at 95%, 2-sided.

Unless specified otherwise, efficacy and safety will be assessed using the modified intent-to-treat (mITT) population, and data will be analyzed based on the assigned treatment (that is, not the actual treatment received by the participant). For submission to the US FDA to support the registration of tirzepatide for chronic weight management, the primary efficacy analysis will be conducted using the Full Analysis Set (FAS). For other purposes, the efficacy analysis of the double-blind period will be conducted using the Efficacy Analysis Set (EAS). Safety analysis of the double-blind period will be conducted using the Safety Analysis Set (SS).

Unless otherwise specified, for analyses in the double-blind period, baseline is defined as the last nonmissing data collected prior to or at randomization (prior to the first dosing of study drug). For analyses in the lead-in period, baseline is defined as the start of screening and ends prior to the intensive lifestyle modification program (typically at Week -12).

Summary statistics for continuous measures will include sample size, mean, standard deviation (SD), median, minimum, and maximum. The analysis model to make comparisons among treatment groups relative to continuous measurements assessed over time will be either analysis of covariance (ANCOVA) or an MMRM, with terms of treatment, visit, treatment-by-visit interaction, stratification factors, and corresponding baseline measurement as a covariate. An unstructured covariance structure will model the relationship of within-patient errors.

The Kaplan-Meier method will be used for estimation of cumulative event-free survival rates over time, and Cox proportional hazards regression analysis will be used to compare hazard rates among treatments.

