4.3.2.2. The Analysis Related to the Efficacy Estimand

The analysis related to the efficacy estimand will be conducted utilizing data in the EAS.

For the mean percentage of body weight change from randomization, an MMRM will be conducted. Restricted maximum likelihood (REML) will be used to obtain model parameter estimates, and the Kenward-Roger option will be used to estimate the denominator degrees of freedom. The response variable of MMRM will be the percent change in body weight from baseline values obtained at each scheduled postbaseline visit.

For the percentage of participants achieving at least 5% body weight reduction from randomization to the 72 weeks visit, a logistic regression model will be used with the response variable of the percentage of participants achieving at least 5% body weight reduction (Yes or No), with the missing value imputed using the predicted value from MMRM analysis followed by dichotomization. The terms for the logistic regression model will be the same as those for the treatment regimen estimand.

For the MMRM model, the independent variables of analysis model are treatment group, visit, and treatment-by-visit interaction; stratification factors (country and sex) as fixed effects; and baseline body weight as a covariate. An unstructured covariance structure will model the relationship of within-patient errors. If this model fails to converge, the following variance-covariance structures will be tested in order until convergence is achieved:

- heterogeneous Toeplitz
- heterogeneous first order autoregressive
- heterogeneous compound symmetry
- Toeplitz
- first order autoregressive, and
- compound symmetry.

The first covariance structure that converges will be used.

With the aid of the MMRM analysis, the 2-sided 95% CI for mean percent change in body weight from randomization to the 72 weeks visit for tirzepatide MTD compared to placebo will be derived and summarized. The resulting least-squares-mean estimates of mean percent change in body weight from baseline will be plotted by visit and by study treatment.

With the aid of the logistic regression model, the 2-sided 95% CI and odds ratio for percentage of participants achieving at least 5% body weight reduction from randomization to the 72-week visit for tirzepatide MTD compared to placebo will be summarized.

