Compare tirzepatide MTD QW with placebo from randomization for improvement of patient-reported outcomes (measured at 72 weeks)	Mean change in SF-36v2 acute form Physical Functioning (PF) domain score from randomization	ANCOVA model	Use terms of treatment, stratification factors, and baseline SF-36v2 PF score as a covariate. Missing data will be imputed using LOCF.
Compare tirzepatide MTD QW with placebo from randomization for improvement of patient-reported outcomes (measured at 72 weeks)	Mean change in IWQOL-Lite-CT PF composite score from randomization	ANCOVA model	Use terms of treatment, stratification factors, and baseline IWQOL-Lite-CT PF score as a covariate. Missing data will be imputed using LOCF.
Compare tirzepatide MTD QW with placebo from Visit 2 for body weight and BMI reduction (measured at 72 weeks)	Mean change in absolute body weight (kg) from Visit 2	MMRM model in Section 4.3.2.2 with body weight at Visit 10 (Week 0) as an additional covariate	LSM estimates through 72 weeks will be plotted by study treatment.
	Mean percent change in body weight from Visit 2	MMRM model in Section 4.3.2.2 with body weight at Visit 10 (Week 0) as an additional covariate	
	Mean change in BMI (kg/m ²) from Visit 2	MMRM model in Section 4.3.2.2 with body weight at Visit 10 (Week 0) as an additional covariate	LSM estimates through 72 weeks will be plotted by study treatment.

Objective	Relative to the Efficacy Measure	Analysis Conducted in a Manner Similar to	Additional Information
Compare tirzepatide MTD QW with placebo from Visit 2 for waist circumference reduction (measured at 72 weeks)	Mean change in waist circumference (cm)	MMRM model in Section 4.3.2.2	LSM estimates through 72 weeks will be plotted by study treatment.

Abbreviations: ANCOVA = analysis of covariance; BMI = body mass index; HbA1c = hemoglobin A1c; HDL-C = high-density lipoprotein cholesterol; IWQOL-Lite-CT = Impact of Weight on Quality of Life-Lite-Clinical Trials Version; LDL-C = low-density lipoprotein cholesterol; LOCF = last observation carried forward; LSM = least squares mean; MMRM = mixed model for repeated measures; QW = once weekly; SF-36v2 = Short Form 36 version 2 Health Survey; VLDL-C = very low-density lipoprotein cholesterol.

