4.6. Safety Analyses

Unless specified otherwise, safety assessments for the double-blind period will be based on the SS (Table GPHM.3.1). All data collected between randomization and the end date of study participation will be included, regardless of the adherence to study drug.

Safety outcomes during the intensity lifestyle modification lead-in period will also be summarized for all enrolled participants. Detailed analyses can be found in Appendix 4 (Section 6.4).

The statistical assessment of homogeneity of the distribution of categorical safety responses between tirzepatide and placebo will be conducted using Fisher's exact test, unless specified otherwise.

The mean change from baseline differences among treatments at all scheduled visits will be assessed via an MMRM using REML. Unless specified otherwise, if the safety parameter is assessed at 72 weeks, then the model will include country/pooled country, sex, percentage of body weight reduction at the end of lead-in ($<10\%$ and $\geq 10\%$), treatment group, visit, and treatment-by-visit interaction as fixed effects and baseline value of the safety parameter as a covariate. To model the covariance structure within participants, the unstructured covariance matrix will be used. If this model fails to converge, the covariance structures specified in Section 4.3.2.2 will be tested in order until convergence is met. If the data do not warrant the MMRM model, then an ANCOVA model will be conducted.

For selected parameters, time-to-first-event analysis via the Cox proportional hazards model may be conducted. Participants without the event will be censored at the end of study participation.

For participants experiencing the event, the “time-to-first-event” will be the time (in weeks) from first dose to first occurrence of the event.

Where necessary, the rate of events will be analyzed using a generalized linear mixed model, assuming the number of events follows a negative binomial distribution, with treatment as a fixed effect. The logarithm of days during the active treatment period will be adjusted as an offset, to account for possible unequal treatment duration of follow-up between participants.

Unless otherwise specified, all the analyses listed in this section will be conducted using up to 72 weeks treatment period, plus the safety follow-up (Visit 801), for all randomized participants.

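### The SAP's primary efficacy models leave out one of the three randomisation strata (lead-in weight loss <10% vs ≥10%), contrary to the protocol and without declaring it

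*SAP*

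**What the plan says.** Protocol 6.3 sets three strata: "The randomization will be stratified by country, sex (female, male), and percent weight loss at the end of lead-in", split at 10%. Protocol 9.4.3.1 specifies the primary models for the hybrid estimand: "Both models (ANCOVA and logistic regression model) will include terms of treatment, stratification factors, and baseline body weight as a covariate". Protocol 9.4.1 gives the general MMRM "with terms of treatment, visit, treatment-by-visit interaction, stratification factors and baseline measurement as a covariate". Neither passage limits which factors are meant.

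SAP 4.3.2.1 names two of the three: "Both models will include terms of treatment group, country/pooled country, and sex as fixed effects and baseline body weight as a covariate". SAP 4.3.2.2 gives its MMRM "stratification factors (country and sex) as fixed effects", and its logistic model takes its terms from 4.3.2.1. The sensitivity analyses (4.3.2.4) and key secondary analyses (Table GPHM.4.2) inherit these models by reference. The subgroup models in 4.7.2.1 repeat the two-factor list.

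Other parts of the SAP read differently:

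- SAP 4.1 describes the general model "with terms of treatment, visit, treatment-by-visit interaction, stratification factors, and corresponding baseline measurement as a covariate", without restriction.
- SAP 4.6 lists for the safety MMRM "country/pooled country, sex, percentage of body weight reduction at the end of lead-in", so all three strata are in.
- Table GPHM.4.3 says for the SF-36v2 Physical Functioning score: "Use terms of treatment, stratification factors, and baseline SF-36v2 PF score as a covariate". Table GPHM.4.4, which covers the same score over Week 0 to Week 72, lists country and sex only. The IWQOL-Lite-CT physical function score has the same mismatch.

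SAP 4.9 records three changes from the protocol: a ≥20% key secondary objective, non-HDL cholesterol, and a region subgroup. The lead-in stratum is not among them, nor is it in the Version 3 change list.

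**The concern.** The protocol defines the primary model one way and the SAP another, with no reason given. The SAP's gloss that the stratification factors are country and sex also misdescribes the trial's own randomisation.

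Three things are at stake.

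- **Continuous endpoints (percent weight change, waist).** Stratified allocation balances the stratum between arms. If the stratum is prognostic, the true variance of the difference is lower than a model without it reports. The standard error is then too large and the test conservative.
- **Logistic endpoints (≥5%, and H2-H5).** The odds ratio is not collapsible. Leaving out a prognostic factor moves the estimate toward 1 and lowers its standard error, with a small net loss of efficiency. SAP 1.1.2.1 makes the odds ratio the population-level summary for the binary co-primary, so the choice of covariates changes what is estimated.
- **H2 (keeping at least 80% of the lead-in loss).** The stratum is tied to the outcome by definition, because the regain allowed grows with the lead-in loss.

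Baseline weight in these models is weight at randomisation. It does not determine percent lead-in loss, so it does not stand in for the stratum.

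**Working it through.** **Inputs from the documents** (Protocol 9.2, SAP 5): 300 per arm, 25% dropout, two-sided alpha 0.05, difference 12 points, SD 10, responders 20% vs 46%. **Assumed, because the documents do not give them:** the share p with ≥10% lead-in loss (0.15-0.40) and the difference b in outcome between strata (0-6 points), with total SD held at 10.

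**1. The plan's own power.** 300 × 0.75 = 225 per arm. SE = 10 × √(2/225) = 0.943, and 12/0.943 = 12.7, so power exceeds 99.99%. For 20% vs 46% the chi-square power is 0.99998. The stated power above 90% is reproduced for both endpoints.

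**2. Continuous endpoints, complete data.** Ratio of reported to true SE = √(100/(100 − p(1−p)b²)). True alpha = 2(1 − Φ(1.96 × ratio)). Example with p = 0.40, b = 6: p(1−p)b² = 0.24 × 36 = 8.64; √(100/91.36) = 1.046; 1.96 × 1.046 = 2.05; alpha = 0.040.

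| p | b = 0 | b = 2 | b = 4 | b = 6 |
|---|---|---|---|---|
| 0.15 | 1.000 (0.050) | 1.003 (0.049) | 1.010 (0.048) | 1.024 (0.045) |
| 0.25 | 1.000 (0.050) | 1.004 (0.049) | 1.015 (0.047) | 1.036 (0.042) |
| 0.40 | 1.000 (0.050) | 1.005 (0.049) | 1.020 (0.046) | 1.046 (0.040) |

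Entries are the SE ratio, with true alpha in brackets. Simulation with stratified blocks of 4 (n = 450, 8,000 null trials) gave 1.019 and 0.045 at (0.25, 4), and 1.046 and 0.039 at (0.40, 6). Alpha was 0.049 with the stratum in the model. In a separate simulation with a true difference of −12, the mean estimate was −12.00 with or without the stratum. Widening the assumptions to p = 0.5 and b = 8 lowers the SE from 0.943 to 0.864 once the stratum is included, so the interval without it is about 9% too wide. These figures do not carry over directly to the multiply imputed analysis.

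**3. The ≥5% endpoint, 225 per arm.** I used a latent normal outcome with a stratum shift, calibrated to 20% and 46% overall, and took the large-sample logistic fit with and without the stratum. Without it the odds ratio is (0.46/0.54)/(0.20/0.80) = 3.41 throughout.

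| p, b | OR with stratum | SE without it is smaller by | Efficiency lost |
|---|---|---|---|
| 0.15, 2 | 3.42 | 0.2% | 0.2% |
| 0.25, 4 | 3.48 | 0.9% | 1.3% |
| 0.40, 6 | 3.63 | 3.0% | 4.1% |

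Simulation (1,500 trials per scenario) agreed within its error and put power at 99.9% or more either way.

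**4. H2.** After a lead-in loss L (as a fraction of starting weight), Week 0 weight is 1 − L of the start. The regain still counted as success, as a percentage of Week 0 weight, is 100 × 0.2L/(1 − L): 1.05% for L = 5%, 2.22% for 10%, 3.53% for 15%. As an illustration, a 20% placebo responder rate with SD 10 under normality implies a placebo mean of −5 + 10 × 0.8416 = +3.42%. Placebo H2 response would then be Φ((regain − 3.42)/10) = 41%, 45% and 50%, if change after randomisation did not depend on lead-in loss.

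**The case against.** **The term may not be used inconsistently.** SAP 4.3.2.2 glosses it once, as country and sex. On that reading Tables GPHM.4.3 and GPHM.4.4 agree, and the safety MMRM simply has its own list. But that reading contradicts the randomisation in Protocol 6.3, and the reading that respects the randomisation puts the two tables in conflict. A programmer cannot tell which is meant.

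**The protocol's explicit list is narrower than it looks.** Protocol 9.4.3.1 gives terms only for the hybrid-estimand ANCOVA and logistic models. The MMRM terms come from 9.4.1, and none are listed for the longitudinal logistic model. This is correct, but it leaves the treatment-regimen co-primary models and the MMRM in conflict.

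**Silence in 4.9 is not by itself a breach.** Protocol 9.4.1 lets non-principal changes be explained in the SAP or the study report, and the Version 2 change details are not in the documents, so nothing can be said about them. Even so, SAP section 1 names 4.9 as the place for such changes.

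**The stratum is already examined.** SAP 4.7.2.1 has lead-in loss as a subgroup for both co-primary endpoints. That shows whether the stratum matters but leaves the primary model unchanged.

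**The effect is small and assumption-driven.** This stands: at b = 0 there is no effect on precision. The H2 response rates are also fragile. Under the same normal model, 20% vs 46% implies a 7.4-point difference, while 12 points implies about 64% responders, so the planning assumptions do not fit it jointly. If larger losers regain more, the gap shrinks or reverses. The regain allowances follow from the definition and do not depend on that model.

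**Conclusion.** The concern holds. The SAP's primary and key secondary efficacy models omit a factor used in the randomisation, which the protocol's stated primary models include. The SAP does not use the term for these factors consistently, and neither 4.9 nor the Version 3 list declares the change.

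It does not threaten the trial's conclusion: the cost is slight conservatism and a somewhat different conditional odds ratio for a co-primary endpoint. The sizes rest on the assumed stratum share and effect, and on complete data for the continuous endpoints. The case for acting is that the primary model should have one definition, and that adjusting for a factor already used to randomise costs almost nothing. It should be corrected, but it is not critical.

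**What to change.** - Add lead-in percent weight loss (<10%, ≥10%) as a fixed effect to the ANCOVA and logistic models in SAP 4.3.2.1 and to the MMRM in 4.3.2.2. SAP 4.3.2.4 and Table GPHM.4.2 follow by reference and need no edit.
- Add it to the subgroup models in 4.7.2.1, except those for the lead-in-loss subgroup, where it is constant or already the subgroup term.
- Define the stratification factors once in SAP 4.1 and use that list in Tables GPHM.4.3 and GPHM.4.4.
- SAP 4.3.2.3 names no covariates for the imputation model. When they are specified, state whether the stratum is among them, so that imputation and analysis match.
- If the two-factor model is intended, declare and justify it in SAP 4.9 and correct the gloss in 4.3.2.2.

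The cost is SAP wording and one model term. The stratum is already in the IWRS for every randomised participant, and the sample size and power statements do not change.
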